2.5.2 Extension phase

Period in the Extension Phase (EP)	EP Basel	ine Period		EP Treatment Period	[EP Wash-Out Period	EP Treatm	nent Period II	EP Early Term.
Duration of the whole period	1 Day	1 Day		1 Year	2	6 Weeks	1	Year	1 Day
Visit number	Visit 7A ⁱ	Visit 7B	Visit 8	Visit 9A	Visit 9B	Visit 10	Visit 11	Visit 12 / EOS	ET
Name of the Visit	EP Screening/Bsl	EP Baseline	EP Treatment 1	EP Treatment 2	EP Treatment 2	EP Washout 1	EP Treatment 3	EP Treatment 4	EP ET
Timeline (Days)	Day -1	Day 1, Start IMP	Day 180	Day 365	Day 366	Day 407	Day 587	Day 767	XX
Visit Window allowed	na	+6 day"	+/- 14 days	+/- 14 days	na	+14 days	+/- 14 days	+/- 14 days	na
Patient information and informed consent process	х					x			
Inclusion / exclusion criteria	X								
Patient Weight		х	X		х	Х	x	х	X
Physical Examination		х	X		X	Х	x	x	X
Documentation of concomitant medication	х		x		х	x	x	х	x
Documentation of frequency of therapy (hours per week)	x		x		x	x	х	х	x
Vital signs	X		X		х	Х	X	Х	X
12-lead electrocardiogram (ECG)				X					X
Blood safety laboratory tests ⁱⁱⁱ	X		X		X	Х	X	X	X
Blood samples for research purposes	x				X			х	x
PK Blood Sampling ^{iv}		x			X				
Urinalysis	X		X	x		Х	x	x	X
Urine by dipstick for pregnancy test ^v	X		X	X		Х	x	х	X
Urine test for N-Acetyl-D-Leucine	X					Х			X
Quality of Life EQ-5D-5L for patients aged ≥18; EQ-5D-Y for children aged <18 years ^{vi}	x		x	x		x	x	X	x
Scale for Ataxia Rating (SARA)	X		X	X		Х	х	X	X

Intra BIO

Clinical Study Reference: IB1001-202

Scale for Spinocerebellar Ataxia Functional Index (SCAFI)	x		x	x		х	x	х	x
Video-Recording Primary Anchor Tests (8MWT + 9HPT-D)	X ^{vii}		x	x		x	x	X	X
Modified Disability Rating Scale (mDRS)	x	x	x	x		х	x	X	x
Clinical Global Impression of Seventy (CGI-S) by Physician	x	x	x	x		х	x	x	x
Clinical Global Impression of Sevenity (CGI-S) by Caregiver	x		x	х		х	х	х	х
Clinical Global Impression of Seventy (CGI-S) by Patient	х		x	x		х	x	х	x
Clinical Global Impression of Change (CGI-C) by Physician			x	x		x	х	X	х
Clinical Global Impression of Change (CGI-C) by Caregiver			x	x		х	x	x	x
Clinical Global Impression of Change (CGI-C) by Patient			x	х		х	x	X	x
Documentation of AEs	X	X	X	X	X	X	X	X	X
Dispensing of study drug		X	X			Х	X		
Intake of study drug at site		х			х				
Return of study drug ^{viii}			X		X		X	X	X
Study drug compliance check			X		X		X	X	X

Abbreviations: EP = Extension Phase; na = not applicable.

ⁱ Visit 7A may be taken from Visit 6, provided Visit 7B is scheduled within 1 day (+6 days) of Visit 6

ii f Visit 7B cannot be scheduled 1 day (+6 days) after Visit 6, Visit 7A and Visit 7B should be conducted over a two-day period on two consecutive days, i.e. Visit 7B occurs +1 day after Visit 7A

iii Analyzed at central lab

^{iv} Analyzed at PK lab

^v Only for women of childbearing potential; done at site

vi If a patient turns 18 over the course of the study, they should continue to use the EQ-5D-Y

vii If Visit 7A is based on Visit 6 assessments, the video recordings from Visit 6 should be used

viii Or after visit if IMP is returned via courier

ix If applicable

General note: due to COVID-19, deviations from the schedule of visits and assessments may be necessary. Any changes to the schedule of visits/assessments should be discussed between the PI and

Clinical Study Reference: IB1001-202

3 SUBJECTS FOR ANALYSIS

3.1 Parent study: Analysis populations

3.1.1 Intention-to-Treat (ITT) population

The ITT population will consist of all patients who receive at least one dose of study drug (N-Acetyl-L-Leucine) and with one video recording at either Visit 1 or Visit 2 (or both).

3.1.2 Modified Intention-to-Treat (mITT) population

The mITT population will consist of all patients who receive at least one dose of study drug (N-Acetyl-L-Leucine) and with one video recording at either Visit 1 or Visit 2 (or both) and one video recording at either Visit 3 or Visit 4 (or both).

3.1.3 Per Protocol Set (PPS)

The PPS will consist of all patients with at least one video recording at baseline (either Visit 1 or Visit 2), end of treatment (either Visit 3 or Visit 4), and end of washout (either Visit 5 or Visit 6) and without any major protocol deviations that can influence the validity of the data for the primary efficacy variable.

3.1.4 Safety Analysis Set (SAF)

The Safety Analysis Set (SAF) will consist of all patients who receive at least one dose of study drug (N-Acetyl-L-Leucine).

3.2 Extension phase: Analysis populations

The Extension phase will only include patients who completed Visit 6 of the Parent study and fulfill the inclusion criteria of Extension phase. Patients who completed Visit 10 of the Extension phase and are willing to continue for an additional year will continue in the Extension Phase until Visit 12.

3.2.1 Modified Intention-to-Treat Extension phase (mITTe) population

The mITTe population will consist of all patients who receive at least one dose of study drug (N-Acetyl-L-Leucine) in Extension phase and with a mDRS score at Visit 7 and at either Visit 8 or Visit 9 (or both). This analysis population will be used for efficacy analyses throughout the Extension phase until Visit 12.

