7.1.7 Extension Phase Early Termination (ET)

- Return of trial drug and compliance check
- Documentation of frequency of therapy (hours per week)
- Documentation of concomitant medication
- Vital signs
- Physical examination
- Weight
- Spinocerebellar Ataxia Functional Index (SCAFI) + Video-Recording of Clinical Impression of Change in Severity (CI-CS) Anchor Tests (9HPT-D and 8MWT)
- Scale for Assessment and Rating of Ataxia (SARA)
- Modified Disability Rating Scale (mDRS)
- Quality of Life EQ-5D-5L for patients aged \geq 18 years, EQ-5D-Y for patients aged <18 years
- Clinical Global Impression of Severity (CGI-S) by physician
- Clinical Global Impression of Severity (CGI-S) by caregiver
- Clinical Global Impression of Severity (CGI-S) by patient *if able*
- Clinical Global Impression of Change (CGI-C) by physician based on previous visit
- Clinical Global Impression of Change (CGI-C) by caregiver based on previous visit
- Clinical Global Impression of Change (CGI-C) by patient *if able* based on previous visit
- 12-lead ECG
- Urinalysis (done at central lab)
- Urine by dipstick: pregnancy test for women of childbearing potential (done at site)
- Urine test for N-Acetyl-D-Leucine (done at PK lab)
- Blood draw for safety laboratory tests (done at central lab)
- Blood draw for research purposes
- Documentation of adverse events.

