8.1.2 Analysis Populations

- The Safety Analysis Set Extension Phase (SAFe) will consist of all patients who receive at least one dose of study drug (N-Acetyl-L-Leucine) in the Extension Phase
- The modified intention-to-treat Extension Phase analysis set (mITTe) will consist of all patients in the SAF with a modified Disability Rating Scale score at Visit 7 of the Extension Phase and either at Visit 8 or Visit 9 (or both)

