8.5.1 Primary Efficacy Endpoint

The primary endpoint is based on the modified Disability Rating Scale (mDRS) score with success defined as no change or a decrease in the mDRS score from Visit 7 to Visit 9.

It is postulated that under standard of care, 90% of patients would worsen (higher score) in terms of their performance on the mDRS scale over a 12-month period, while conversely only 10% would show similar performance or some improvement. Statistical evaluation of the primary binary endpoint (success/failure on mDRS scale) will compare the proportion of success with 10% in a one-sided Fishers Exact test at the one-sided 5% significance level.

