2.4.2 Extension phase

The sample size is determined by the number of patients that move into this Extension phase from the Parent study. The expectation is that between 60% and 70% of patients will rollover into the extension period. With 20 out of 32 patients (62.5%) rolling over, the study will have 80% power to detect an improvement in the success rate to 31% compared to the null hypothesis value of 10%.

Patients who completed Visit 10 of the Extension phase and are willing to continue for an additional year will continue in the Extension Phase until Visit 12.

Clinical Study Reference: IB1001-202

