6.6 Statistical analysis efficacy endpoints

The analysis for all efficacy endpoints in the Extension phase is the mITTe.

Analyses of the primary endpoint based on the mITTe population will utilise a last observation carried forward (LOCF) approach for missing mDRS at Visit 9. For the primary mDRS endpoint this implies that the measurement of Visit 8 will be used instead. Other endpoints will not be imputed, and missing data will be reported as is. No sensitivity analyses will be applied.

For the primary endpoint for the Extension phase there will be separate descriptive statistical displays within the key subgroups as listed in Section 6.5.3, without any statistical analysis. For the subgroup presentations, only the mITTe population will be used. No plots will be created. All individual primary endpoint data will be listed as well.

All efficacy endpoints for Extension phase Visit 10 to Visit 12 are considered exploratory, and therefore described under section 6.6.4.

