6.6.1 Primary endpoint Extension phase

The primary efficacy endpoint is based on the Modified Disability Rating Scale (mDRS). The mDRS measures neurological status via clinical signs and symptoms in 6 domains (ambulation, language, manipulation, swallowing, seizures, and ocular movement). A higher mDRS score indicates a clinical worsening, while a lower mDRS score indicates a clinical improvement. A 0-point change in the mDRS score represents a stabilization of disease progression, which is also considered a significant clinical improvement.

The mDRS composite score and individual domains, including change values, will be summarized using descriptive statistics at each visit for Extension phase.

The primary endpoint in this Extension Phase is success measured on the mDRS score from the Extension Phase baseline (Visit 7) to the end of treatment in the Extension Phase (Visit 9). Success is defined as no change or a decrease in mDRS score from Visit 7 to Visit 9.

The primary endpoint will be summarized using a frequency table. The primary statistical analysis of comparing the proportion success with the null proportion of 0.10 will be done using a one-sided Fisher's Exact Test, expecting an increase in the success rate. The statistical result (one-sided p-value and exact 90% confidence interval²) will be added to the frequency table. This analysis is considered to be exploratory.

In addition, a spaghetti plot presenting the total mDRS scores of each patient through time will be created.

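### Extension patients who leave the study or die before Visit 8 drop out of the mDRS success-rate denominator, and no supplementary analysis shows the effect

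*SAP*

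**What the plan says.** SAP 3.2.1 admits to mITTe dosed Extension patients "with a mDRS score at Visit 7 and at either Visit 8 or Visit 9 (or both". Protocol Appendix 6, 8.1.2, has the same requirement: "with a modified Disability Rating Scale score at Visit 7 of the Extension Phase and either at Visit 8 or Visit 9 (or both". SAP 6.6 makes mITTe the set for every Extension efficacy endpoint.

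SAP 6.6.1 defines the endpoint: "Success is defined as no change or a decrease in mDRS score from Visit 7 to Visit 9". The analysis is then "comparing the proportion success with the null proportion of 0.10 will be done using a one-sided Fisher's Exact Test". Protocol Appendix 6, 8.5.1, sets the level: "in a one-sided Fishers Exact test at the one-sided 5% significance level". It bases the 10% on a postulate that 90% of patients under standard of care would worsen on the mDRS over 12 months.

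For missing data, SAP 6.6 replaces a missing Visit 9 mDRS with the Visit 8 value and goes no further: "Other endpoints will not be imputed, and missing data will be reported as is. No sensitivity analyses will be applied". Protocol Appendix 6, 8.6, agrees. Visit 8 falls at Day 180, plus or minus 14 days.

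The Extension Early Termination (ET) visit in Protocol Appendix 6, 7.1.7, lists "Modified Disability Rating Scale (mDRS"), and the schedules of events mark it too. No rule brings that value into the success endpoint. SAP 6.3 says in general terms that data from withdrawn patients enter the analysis up to their last assessment. That sits awkwardly with a set definition that removes the earliest of them altogether.

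**The concern.** The 10% null is a fixed external figure for a 12-month course. The observed rate is computed only among patients who stayed long enough to have a Visit 8 or Visit 9 mDRS, so it is conditional on staying about six months. In a progressive, life-threatening disease, leaving early or dying is plausibly related to worsening. Taking such patients out of the denominator while leaving the null unchanged raises the observed rate, and there is no concurrent arm in which the same selection would operate.

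At about 20 patients the exact test is coarse. One or two patients in or out of the denominator can decide which side of 5% the p-value falls on.

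**Working it through.** **Inputs.** Null rate 0.10, one-sided 5% (Protocol Appendix 6, 8.5.1; SAP 6.6.1). Planned size and power: "With 20 out of 32 patients (62.5%) rolling over, the study will have 80% power" to detect 31% (SAP 2.4.2). Expected rollover is 60% to 70%; applied to 32 patients this is 0.60 × 32 = 19.2 to 0.70 × 32 = 22.4, so about 19 to 22 entrants. The number leaving before Visit 8 is not given. I use 2 as an illustration and look at 1 to 4.

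**Test.** Fisher's exact test compares two samples. Against a fixed proportion I read it as the exact binomial test, p = P(X ≥ s | n, 0.10).

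**The plan's own figure.** At n = 20 the smallest significant count is 5: P(X ≥ 5 | 20, 0.10) = 0.0432, whereas P(X ≥ 4 | 20, 0.10) = 0.133. Power is P(X ≥ 5 | 20, 0.31) = 0.791. The stated 80% is reproduced.

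**Effect of the denominator.** Early leavers are either excluded (as planned) or kept as non-successes:

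| Dosed | Leave before Visit 8 | Successes | As planned | Leavers kept |
|---|---|---|---|---|
| 22 | 2 | 5 | 5/20, p=0.0432 | 5/22, p=0.0621 |
| 21 | 1 | 5 | 5/20, p=0.0432 | 5/21, p=0.0522 |
| 20 | 2 | 5 | 5/18, p=0.0282 | 5/20, p=0.0432 |
| 20 | 2 | 4 | 4/18, p=0.0982 | 4/20, p=0.1330 |
| 19 | 2 | 5 | 5/17, p=0.0221 | 5/19, p=0.0352 |
| 19 | 2 | 4 | 4/17, p=0.0826 | 4/19, p=0.1150 |

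The result changes at 21 and 22 dosed because the critical count falls from 6 to 5 once the set shrinks to 20 or fewer. At 19 and 20 dosed the critical count is 5 with or without the two leavers, so nothing changes.

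**Type I error, worst case.** Suppose the true rate among all N dosed is 10% and all k leavers are non-successes. The rate among those analysed is then 0.10N/(N − k), and the error is P(X ≥ critical count | N − k, that rate).

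- 22 dosed, 2 leavers: rate 2.2/20 = 0.110, error 6.1%. With 3 or 4 leavers it is 6.0%. With 1 leaver it is 1.8%, because the critical count is still 6.
- 21 dosed, 1 to 4 leavers: 5.2% down to 5.0%.
- 20 dosed, 1 to 4 leavers: 4.3% down to 4.1%.
- 19 dosed, 1 to 4 leavers: 3.5% down to 3.3%.

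Within the planned 19 to 22 entrants and up to 4 leavers, the maximum is about 6%.

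**Why the ET value should not simply be carried forward.** If both leavers in the 22-patient example were stable at a short ET visit and scored as successes, the result would be 7/22, p = 0.0044. That credits brief follow-up as 12-month success.

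**The case against.** The strongest reply is that little turns on this test. SAP 6.6.1 calls it exploratory, SAP section 7 lets trial success depend only on the Parent endpoint, and both documents say conclusions will not rest on significance alone. Entrants are also selected: they completed Visit 6, and the investigator judged further treatment to be in their interest, so early losses may be few. The planned disposition table and the listings of exclusion reasons and individual mDRS scores would let a careful reader rebuild most of the fuller analysis. All of this stands. It limits the weight of the point but does not put the missing patients into any planned summary.

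A second reply is that withdrawal need not mean worsening. The withdrawal reasons in Protocol 4.3 include pregnancy, loss to follow-up and pandemic complications, and the 10% postulate says nothing about how deaths or withdrawals count. Scoring every early leaver as a non-success is therefore itself an assumption. It also treats a patient leaving just before Visit 8 differently from one leaving just after with a stable score, who remains a success by carry-forward. This also stands. It is why the fuller analysis belongs beside mITTe and not in its place.

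Three stronger readings are tempting but unsupported:

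- A reader might infer that anyone who stops drug is dropped. Protocol 4.3, which Appendix 6, 4.2 applies to the Extension, asks such patients to keep attending visits; those who attend Visit 8 stay in mITTe.
- A reader might infer that the ET visit supplies an mDRS for every early leaver. Patients who die have no ET visit.
- A reader might take the Parent plan's 39 enrolled and 36 in mITT as an early on-treatment loss rate of 8%. The documents do not say those three were dosed, and patients can leave before dosing, for example on the Visit 1 urine result.

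**Conclusion.** The gap is real and modest. Dosed Extension patients who leave the study or die before Visit 8 are absent from the success rate, and the plan provides no analysis that includes them. The direction of bias is upward if they are mainly non-successes; the documents can neither confirm nor exclude that, and they give no dropout rate.

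It would be too strong to say that two early leavers overturn the result at the planned size. The plan has 20 entering, and at 19 or 20 dosed two exclusions leave the conclusion unchanged. At 21 dosed one is enough, and at 22 two are. An error of 8.3% can be produced with 24 entrants and 4 leavers (rate 2.4/20 = 0.12), but 24 lies outside the 60% to 70% rollover of 32. Within the planned range the worst case is about 6%, and it requires every leaver to be a non-success.

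These figures use the unadjusted exact p-value. The SAP applies a mid-p adjustment only to the confidence interval; a mid-p test would give 0.040 for 5/22, so the illustrated change at 22 dosed depends on the plain exact test.

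**What to change.** Keep the mITTe result and add to the SAP, for the Extension success endpoint only:

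1. A named supplementary analysis of the success rate in all dosed Extension patients with a Visit 7 mDRS, counting death or study withdrawal before Visit 8 as not a success. Use the same exact test and interval.
2. Removal, for this endpoint, of the statement that no sensitivity analyses will be applied. Record the departure from Protocol Appendix 6, 8.6, in SAP section 7.
3. A listing of each early leaver's reason for leaving and, where an ET visit took place, the mDRS change from Visit 7, without carrying that value forward as a success.
4. A sentence stating that patients who leave after Visit 8 are still scored by the Visit 8 carry-forward, so that the different treatment is explicit, and one reconciling SAP 6.3 with the mITTe definition.

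The cost is a few lines of SAP text and one extra row in the success-rate table. The supplementary rate may be lower than the mITTe rate. If nobody leaves before Visit 8 and no dosed patient otherwise lacks both later scores, the two rows are identical.

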3.2.2 Safety Analysis Set Extension phase (SAFe)

The SAFe will consist of all patients who receive at least one dose of study drug (N-Acetyl-L-Leucine) in the Extension phase. This analysis population will be used for all safety analyses throughout the Extension phase until Visit 12. Only reported data will be used in the analysis.

3.3 Protocol deviations

Major protocol deviators will be identified to the extent possible by individuals responsible for data collection/compliance, and its analysis and interpretation. Any subjects or data values excluded from the PPS/PPSe analysis will be identified, along with their reason for exclusion.

Clinical Study Reference: IB1001-202

3.4 Blinded Data Review Meeting

There will be a BDRM meeting held for the Parent study. No BDRM will be necessary for the Extension phase since no Per Protocol analysis population will be defined then.

The patients will be classified during the BDRM to the analysis populations based upon the protocol deviations. Invitees to this meeting are the Sponsor's Medical Expert, the Sponsor's representative, the Sponsor's Project Manager (PM), the Medical Monitor, the Sponsor statistician, and the statistician, but more roles can be invited if considered necessary. Input to this meeting will be supplied by the involved Data Management provider or the responsible PM at least one week in advance of the meeting: a blinded list of all protocol deviations (including missing and likely erroneous data), with specific detailing and description regarding the deviation, preferably in Excel.

Possible compliance issues and unforeseen or reclassification of categories for missingness of the primary endpoint data will be part of the discussions held at the meeting.

Where possible, this meeting will be held in a blinded manner, that is blind to study outcome data (also for open studies). The goal of this meeting is to reach consensus on minor and major protocol deviations. In case of a major deviation impacting the primary or secondary endpoints, the specific patient will be excluded from the PPS population, either completely or from a specific time point onwards. The meeting must be held prior to database lock.

The decisions taken during this meeting and the reasons for those decisions will be documented by the PM (or a delegate as agreed) and sent for review to all parties involved as soon as possible after the meeting, but before database lock. If all parties involved agree, then the document is finalized, signed and stored in the TMF before database lock.

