3.1.3 Target Number of Patients

- To be enrolled: Approximately 39 patients
- To be analyzed according to the modified Intention to Treat (mITT) analysis: Approximately 36 patients
- To be analyzed according to the Per Protocol Analysis: Approximately 30 patients

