8.1.2 Analysis Populations

- The Safety Analysis Set (SAF) will consist of all patients who receive at least one dose of study drug (N-Acetyl-L-Leucine)
- The intention-to-treat analysis set (ITT) will consist of all patients in the SAF with a video recording at either Visit 1 or Visit 2 (or both)
- The modified intention-to-treat analysis set (mITT) will consist of all patients in the SAF with a video recording at either Visit 1 or Visit 2 (or both) and one video recording at either Visit 3 or Visit 4 (or both)
- The Per Protocol Set (PPS) will consist of all patients with video recordings at baseline (Visit 1 or Visit 2), end of treatment (Visit 3 or Visit 4), and end of washout (Visit 5 or Visit 6) and without any major protocol deviations that could have influenced the validity of the data for the primary efficacy variable.

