2.4 Sample size

2.4.1 Parent study

Under the original protocol, it was postulated that N-Acetyl-L-Leucine will show effectiveness in 30% of patients and this success rate is viewed as being clinically important. Assuming that this group of patients will have scores that are evenly distributed across the values 1 and 2 for the primary endpoint and further that the remaining 70% of patients will have scores that are evenly distributed between the values -1, 0, and 1, the resulting mean score is 0.45 and the standard deviation for the primary endpoint is 1.02. With 30 patients reporting on the primary endpoint, the study will have 76% power to detect a treatment benefit in a 5% one-sided one-sample t-test.

Recruitment will continue until approximately 30 patients complete dosing. The following numbers of patients are foreseen:

- To be enrolled: Approximately 39 patients
- To be analyzed according to the modified Intention to Treat analysis (mITT): Approximately 36 patients
- To be analyzed according to the Per Protocol Set (PPS): Approximately 30 patients

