5.6 Statistical analysis efficacy endpoints

The primary analysis population is the mITT for the primary and all secondary endpoints. Analyses of these endpoints based on the PPS will also be undertaken to provide supplementary information on efficacy. The ITT population will be used only for baseline summary tables.

Analyses of the primary endpoint based on the mITT population will utilise a last observation carried forward (LOCF) approach for missing/unreadable videos at Visit 5 and Visit 6. For the primary endpoint CI-CS, this implies that the CI-CS value for Visit 4 to Visit 6 will be assigned the value 0 (stable) if both videos at Visit 5 and Visit 6 are unavailable.

Also for the key secondary endpoint, Change in Severity Score based on Averaged Clinical Impression of Severity (CI-S), it is assumed that if both videos are missing/unreadable for the baseline (Videos from Visit 1 or 2), treatment (Videos from Visit 3 or 4), or washout (Videos from Visit 5 or 6) period, the change from one period to another will be assigned the value 0 (stable).

Clinical Study Reference: IB1001-202

A sensitivity analysis for missing data will be performed for the statistical analyses to compare patient's outcome on the primary outcome measure and their compliance throughout the study. The robustness of the primary analyses in the mITT analysis set will be assessed as follows:

• If either video for Visit 3 or Visit 4 is available but both videos for Visit 5 and Visit 6 are not available, then the value -1 (worsening) will be used instead of 0 for the CI-CS for Visit 4 to Visit 6 unless the missingness is due to a technical reason (MCAR, e.g. due to machine failure).

For each of the primary and secondary endpoints there will be separate descriptive statistical displays within the key subgroups as listed in Section 5.5.3 without any statistical analysis. For the subgroup presentations, only the mITT population will be used. Spaghetti plots will not be created for the subgroup analyses; these will be presented in forest plots (one for each endpoint, excluding the SARA -, SAFI - and mDRS subscores and excluding the EQ-5D-5L/Y), presenting the mean or (pseudo-)median with a 90% two-sided CI, using a stem at mean or median difference of 0, where applicable. Upon discretion of the programmer, the forest plots may be presented as two plots: one for Visit 4 versus Visit 2 and one for Visit 6 versus Visit 4.

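### SAP 3.4 removes a patient from the per-protocol set for a major deviation that touches only a secondary endpoint; the set's own definition in SAP 3.1.3 and Protocol 8.1.2 keeps that patient

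*SAP*

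**What the plan says.** The PPS is defined in three places, in agreement. SAP 3.1.3 requires at least one video in each of the baseline, treatment and washout periods, and that the patient be "without any major protocol deviations that can influence the validity of the data for the primary efficacy variable". Protocol 8.1.2 has the same content: "without any major protocol deviations that could have influenced the validity of the data for the primary efficacy variable". The synopsis (Protocol Appendix 1) repeats it.

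SAP 3.4 describes the meeting that assigns patients to the analysis sets, and gives a different criterion: "In case of a major deviation impacting the primary or secondary endpoints, the specific patient will be excluded from the PPS population". The sentence goes on to say that this may be "either completely or from a specific time point onwards".

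SAP 3.3 contemplates exclusions at more than one level: "Any subjects or data values excluded from the PPS/PPSe analysis will be identified, along with their reason for exclusion". SAP 5.3 also lets the meeting exclude individual values, and mentions clear measurement errors as a possible case.

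On the role of the set, SAP 5.6 makes the mITT the primary population for the primary and all secondary endpoints and adds: "Analyses of these endpoints based on the PPS will also be undertaken to provide supplementary information on efficacy". Planned sizes are about 36 for the mITT (Protocol 3.1.3) and about 30 for the PPS (SAP 2.4.1).

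**The concern.** A per-protocol set should have one membership rule, fixed before anyone classifies patients. Here the definition and the instruction for applying it differ, and SAP 3.4 is the one the meeting will have in front of it. Followed as written, it can discard a patient's valid primary score because something went wrong with another scale.

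The PPS repeats the primary test (planned Table 14.2.1 covers both mITT and PPS), so the set used there should turn on the validity of the primary score. The trial is open-label, and SAP 3.4 keeps the meeting blind to outcome data only where possible. Documenting each decision records what was done, but does not settle which of the two rules should have been applied.

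**Working it through.** The point rests on comparing text, so the rules come first.

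| Place | Major deviation that removes a patient | Level |
|---|---|---|
| SAP 3.1.3 | one that can affect the primary variable | patient |
| Protocol 8.1.2, synopsis | same | patient |
| SAP 3.4 | one that affects primary or secondary endpoints | patient, or patient from a time point |
| SAP section 7 | no change to the PPS rule listed | – |

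**Where the rules part.** A major deviation falls into one of three cases:

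1. It affects the primary variable: both rules exclude.
2. It affects no endpoint: both rules keep.
3. It affects a secondary endpoint only: SAP 3.1.3 keeps, SAP 3.4 excludes.

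**Can case 3 occur?** The primary endpoint uses Visits 2, 4 and 6; Visits 1, 3 and 5 serve only as substitutes when a video is missing (Protocol 8.6). The key secondary endpoint, averaged CI-S, uses all six visits (SAP 5.6.2). A defective Visit 3 video therefore enters the treatment-period CI-S average while a valid Visit 4 video leaves the primary score intact. Protocol 3.1.2.5.1 itself treats Visits 3 and 5 as not critical to the primary outcome, and Protocol 8.1.1 counts delayed or missed assessments due to COVID-19 as deviations. Whether any of these would be graded major is not stated.

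**Does partial exclusion rescue the primary score?** No. Exclusion from Visit 3 onwards loses Visits 4 and 6. Exclusion from Visit 5 onwards loses Visit 6, and with it the Visit 4-to-6 comparison. SAP 5.6 writes the 0-imputation for that comparison for the mITT only.

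**Power, for illustration only.** Inputs from SAP 2.4.1: mean 0.45, SD 1.02, n = 30, one-sided 5% one-sample t-test. The noncentrality is (0.45 / 1.02) × √30 = 0.441 × 5.477 = 2.42. Power is the probability that a noncentral t with 29 degrees of freedom exceeds the 95th percentile of the central t. This gives 76.3%, which reproduces the stated 76%.

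Suppose k patients in case 3 are lost from a PPS of 30 (k is assumed; the documents give no count):

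| k | n | Power |
|---|---|---|
| 0 | 30 | 76.3% |
| 1 | 29 | 75.0% |
| 3 | 27 | 72.2% |
| 6 | 24 | 67.4% |

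The mITT analysis at n = 36 has 82.9% under the same inputs, whatever k is.

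**The case against.** The case for leaving the text alone has substance. SAP 3.4 concerns major deviations only. Of the types named in Protocol 8.1.1, breached entry criteria, prohibited medication and poor compliance act on the whole patient and would usually bear on the primary variable too. Several secondary endpoints come from the same videos. The two rules may seldom diverge. The meeting seeks consensus, is held before database lock, and ends in a signed, filed record; the primary ratings come from blinded raters. A wider rule would also be coherent for a set that serves all secondary endpoints, had it been declared. All of this limits the size of the problem, but it does not remove the conflict.

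Four stronger readings are tempting, and the documents do not support them.

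- *The PPS is the planned check on the primary result.* It is described as supplementary. The named robustness analysis is the −1 imputation within the mITT (Protocol 8.6, SAP 5.6).
- *The power loss measures the harm.* The 76% is stated for 30 patients reporting the primary endpoint. No power is set for the PPS analysis, and the number of affected patients is unknown.
- *SAP 3.1.3 forbids keeping a patient cut after Visit 4.* For washout it asks for a recording, not a usable one. What removes such a patient is its other condition, when the deviation is major and affects the primary variable.
- *A patient cut after Visit 4 has no PPS primary score.* SAP 5.6 limits the imputation to the mITT, but SAP 10.1 says the carried-forward video comparison is already in the delivered data. PPS handling is unclear rather than settled.

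**Conclusion.** The conflict is real: SAP 3.4 is wider than SAP 3.1.3, Protocol 8.1.2 and the synopsis, and section 7 does not declare the difference. Applied as written, it can drop a valid primary score from the PPS primary test for a reason unrelated to that score.

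The size is minor. The mITT primary result is untouched, the affected analysis is supplementary, and the number of patients in the disputed case cannot be derived from the documents. The conclusion assumes only that at least one major deviation could be confined to a secondary endpoint. The plan allows for this, without saying how often it would happen. It does not depend on the power figures.

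**What to change.** In SAP 3.4, replace the reference to primary or secondary endpoints with the primary efficacy variable, as in SAP 3.1.3.

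For a major deviation confined to a secondary endpoint, exclude the affected values from that endpoint's PPS analysis and keep the patient in the set. SAP 3.3 and 5.3 already foresee value-level exclusion; one sentence should say that it covers this case and is documented before database lock.

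Keep the time-point clause only for visit-level secondary data. Deleting it outright could discard valid Visit 2-to-4 data because of a washout-only deviation. State that a patient whose Visit 4-to-6 comparison is excluded for a major deviation is not in the PPS primary-endpoint analysis. This follows from SAP 3.1.3 and from the mITT-only imputation in SAP 5.6.

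If the sponsor does want the wider rule, it belongs in SAP 3.1.3 and should be listed in section 7 as a change from the protocol, accepting that valid primary scores will then be lost from the PPS test.

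The cost is one changed phrase and two or three added sentences in the SAP, with no new data and no new analysis. It should be done before patients are classified.
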